- (‘Directly identifiable’ means that identifiers like name, medical record number, social security number, etc. are included in/attached to the dataset/specimens. Maintaining identifiable data for future research is treated as a registry by the VCU IRB. The IRB must approve the new research use in an amendment to this study or as part of a new study before the project is initiated. You will be asked more questions about this on a later page)*

Will use de-identified or indirectly identifiable information or specimens.

- (‘De-identified’ means that a linkage/key code exists that links identifiers to data/specimens. When the researcher holds both the data and the key, the VCU IRB considers the subjects to be readily identifiable. Maintaining identifiable data for future research uses is treated by the IRB as a registry. The IRB must approve the new research use in an amendment to this study or as part of a new study before the project is initiated. You will be asked more questions about this on a later page)*

Will use anonymized information or specimens.

- (‘Anonymized’ means that 1) no linkage/key codes exist that link identifiers to data/specimens; and 2) subjects cannot be readily identified, i.e. no direct or indirect identifiers or identifiable combinations of variables. The VCU IRB considers uses of anonymized data/specimens to not be human subject research.)*

Will use aggregate results (summary-level results), not individual-level information or specimens.

- (The VCU IRB considers uses of aggregate data to not be human subject research because there are no individual subjects.)*

Will contribute to an existing registry or repository

- (You will be asked more questions about this on a later page.)*

- Will not use information/specimens for purposes beyond this study.**
- Not sure and will submit an amendment when known
- Other use(s) of individual-level information in a way not listed above

5. * Select the way(s) the VCU PI/study team may share individual-level information or biospecimens (including DNA) with other researchers who are not on this study team (i.e. for analyses beyond/apart from the aims of

this study).

See help text for definitions.

Will share directly identifiable information or specimens with other researchers.

- (*'Directly identifiable' means that identifiers like name, medical record number, social security number, etc. are included in/attached to the dataset/specimens. Maintaining identifiable data for future research uses is treated by the VCU IRB as a registry. The data recipient's use of identifiable data would require them to obtain IRB review. You will be asked more questions about this on a later page.*)

Will share de-identified or indirectly identifiable information or specimens with other researchers.

- (*'De-identified' means that a linkage/key code exists that links identifiers to data/specimens. The VCU researcher maintains the key but does not share it with any other researchers. The recipient's use of de-identified data/specimens may not be human subject research if there is documentation that the key will never be shared with the recipient, but they should check with their own IRB about review requirements. You will be asked more questions about this on a later page.*)

Will share anonymized information or specimens with other researchers.

- (*'Anonymized' means that 1) no linkage/key codes exist that link identifiers to data/specimens; and 2) subjects cannot be readily identified (i.e. no direct or indirect identifiers or identifiable combinations of variables). The VCU IRB considers uses of anonymized data/specimens by other researchers to not be human subject research, but the recipient should check with their own IRB about review requirements.*)

Will only share aggregate results (summary-level results), not individual-level information or specimens.

- (*The VCU IRB considers uses of aggregate data to not be human subject research because there are no individual subjects. The data recipient should check with their own IRB about review requirements.*)

Will contribute to an existing registry or repository (You will be asked more questions about this on a later page.)

Will submit data to an NIH genomic data repository (You will be asked more questions about this on a later page.)

Will not share information/specimens with other researchers.

Not sure and will submit an amendment when known

Other sharing of individual-level information with other researchers

6. * The Principal Investigator certifies that after the study has been closed with the VCU IRB, the following conditions will be met whenever individual level research information and/or specimens are used or shared:

- The identities of participants who are represented in the dataset/specimens will not be readily ascertainable or otherwise re-identifiable by the recipient;
- If a linkage/code key is created, it will be maintained at VCU and not shared with the recipient under any circumstances;
- The PI will have no knowledge that the remaining information could be used alone or in combination with any other information to identify the individuals represented in the data; and
- The PI agrees to abide by this sharing plan even after the study has been closed with the VCU IRB.

Yes

No

N/A - No sharing will occur

ID: HM20022338

View: SF2 - Pertinent and Incidental Findings

Pertinent and Incidental Findings

1. * Is it likely investigators could discover a participant's previously unknown condition (e.g. pregnancy, disease, suicidal thoughts, wrong paternity, genetic results, or other findings that may be of importance to health or well-being) or if a participant is engaging in illegal or reportable activities:

 Yes No

ID: HM20022338

View: SF2 - Risk Benefit Complete

Risk Benefit Complete

Protocol Progress:

- ? INITIAL SETUP
- ? BACKGROUND, RATIONALE & GOALS
- ? RESEARCH PLAN
- ? CONSENT PLAN
- ? RISKS, PRIVACY & CONFIDENTIALITY
- ? POPULATIONS WITH SPECIAL CONSIDERATIONS
- ? INSTITUTIONAL REQUIREMENTS
- ? DOCUMENTS

Click Continue below to go to the next section

ID: HM20022338

View: SF2 - Populations with Special Considerations

Populations with Special Considerations

1. * Check all participant groups that will be either
- a) Specifically included in this study or
 - b) Discernable in the research data/specimens.

(Selections will branch)

- Children
- Emancipated minors
- Wards of the State
- Pregnant women or fetuses
- Neonates or Post-delivery Materials
- Prisoners

- Decisionally Impaired Adults
- VCU / VCUHS students or trainees
- VCU / VCU Health System employees
- Individuals with limited English proficiency**
- Active military personnel
- Student populations in K-12 educational settings or other learning environments
- Members of a federally recognized American Indian and Alaska Native tribe
- None of the Above

ID: HM20022338

View: SF2 - Limited English Proficiency

Limited English Proficiency

1. *** Describe how Non-English speaking or limited English proficiency participants will be able to communicate with the study staff at enrollment and throughout the study. Include the following information:**
 - *how the initial informed consent process will be handled*
 - *how the research team plans to interact with LEP participants throughout the conduct of the study*
 - *whether there will be a qualified interpreter or assistive translational devices available*
 - *whether the study consent document will be translated or a short form consent document will be used*
 - *the names of the individuals or professional groups who will provide oral interpretation or written translation services*

If potential study participants have limited English proficiency, the clinical research coordinator will use VCU Health language and communication services to ensure that the patient fully understands the study, and fully consents to be a participant in the study. Free interpreters are available to help the patient and health care providers communicate with one another. A two-handset telephone is available to assist limited-English-proficient patients and their families in communicating with staff and health care professionals. The study consent document will not be translated into languages. A short form consent in the participant's native language will also be used.

2. *** Describe any additional risks or harms to the individual because of their limited English proficiency and how these will be minimized.**

Apart from ensuring full understanding of consent documents, all other study participation will be part of the normal standard of care that they receive by their health care providers.

3. **If an interpreter or translator will be involved in the study, upload documentation verifying qualifications.**

ID: HM20022338

View: SF2 - Populations with Special Considerations Section Complete

Populations with Special Considerations Section Complete

Protocol Progress:

- ? INITIAL SETUP
- ? BACKGROUND, RATIONALE & GOALS
- ? RESEARCH PLAN
- ? CONSENT PLAN
- ? RISKS, PRIVACY & CONFIDENTIALITY

- ? POPULATIONS WITH SPECIAL CONSIDERATIONS
- ? INSTITUTIONAL REQUIREMENTS
- ? DOCUMENTS

Click Continue below to go to the next section

ID: HM20022338

View: SF2 - Study Funding

Study Funding

1. * Have you applied for funding:

Yes

No

2. Is this study already funded:

Yes

No

3. * Select all funding sources for this study (pending or awarded):

Industry

Direct Federal

Indirect Federal

State/Local Government

Non-Profit - Sponsored Project

Non-Profit - Gift

Internal Grant

Investigator/Departmental Funds

None

Other

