View: SF2 - Consent Plan Complete

Consent Plan Complete

Protocol Progress:

- ? **INITIAL SETUP**
- ? **BACKGROUND, RATIONALE & GOALS**
- ? **RESEARCH PLAN**
- ? **CONSENT PLAN**
- ? **RISKS, PRIVACY & CONFIDENTIALITY**
- ? **POPULATIONS WITH SPECIAL CONSIDERATIONS**
- ? **INSTITUTIONAL REQUIREMENTS**
- ? **DOCUMENTS**

Click Continue below to go to the next section

ID: HM20022338

View: SF2 - Risks, Discomforts, Potential Harms and Monitoring

Risks, Discomforts, Potential Harms and Monitoring

1. * **Describe the risks of each research procedure to participants or others. For each identified risk, provide an assessment of the anticipated seriousness and likelihood of the risk. Some examples of possible risks include but are not limited to:**

- **Physical risks (e.g. bodily harms or discomforts, side effects, etc.)**
- **Psychological risks (e.g. emotional, mental, or spiritual harms or discomforts, changes to thoughts, beliefs, or behaviors, etc.)**
- **Research data risks (e.g. loss of confidentiality and privacy)**
- **Social or legal risks (e.g. impacts on relationships or reputation, legal or criminal justice actions for self or others, etc.)**
- **Financial risks (e.g. impacts on income, employability, or insurability, loss of services, etc.)**

- **Other risks (e.g. unforeseeable risks of experimental procedures, risks related to particular study designs (randomization, washout, placebo, withholding care/services, deception), etc.)**

See the help text for additional guidance.

There is a minimal risk of minor pain or discomfort following the procedure resulting from the foam pad placement.

There is minimal risk for the loss of confidentiality and privacy due to the measures that will be taken to maintain privacy and security for data as well as the minimal PHI needed to conduct the study.

There is a minimal risk of jaw and/or neck pain.

SAM may not be as good as usual approach. There is a minimal chance that this is true.

There is minimal chance that as yet unknown risks may occur.

2. * Describe how each of the risks/harms/discomforts identified above will be minimized:

The anesthesia provider will be trained how to properly deploy the device by the clinical research coordinator, ensuring appropriate pad placement. The foam pads are thick enough and will provide enough cushion to prevent soreness along the body of the mandible, where the pads will be deployed.

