The loss of confidentiality and privacy will be mitigated by deidentifying all study participants and maintaining all study documents including patient consent forms under lock and key.

3. * Describe any potential risks or harms to a community or a specific population based on study findings (e.g. information that could be stigmatizing or derogatory):

Not applicable.

4. Where appropriate, discuss provisions for ensuring necessary medical, professional, or psychological intervention in the event of adverse events to the subjects:

Anesthesia expertise in airway management will be directly present for all subjects throughout study procedures and interventions as needed to ensure medical safety will be performed at the discretion of the anesthesia care team, which includes the provider and attending anesthesiologist.

5. * Describe criteria for when the investigator would withdraw an individual participant from the study; such as safety or toxicity concerns, emotional distress, inability to comply with the protocol, etc.:

The study team would withdraw any subjects who demonstrate an inability to comply the study protocol, at the discretion of the anesthesia provider, who will be at their bedside throughout the anesthetic.

6. * Summarize any pre-specified criteria that would trigger the investigator/sponsor/monitoring committee to stop or change the study protocol due to safety concerns:

Three days following their procedure, the clinical research coordinator will follow up with the study participants and ask the following questions:

- Do you have any jaw pain?
- Do you have any neck pain?
- Do you have any head pain?

A telephone script that the CRC will use during these interactions has been uploaded.

If 20% of patients in the SAM intervention arm report pain or neuralgia to their jaw/neck following the procedure, this will trigger a stop with immediate review of the study protocol.

Data and Safety Monitoring

Data and safety monitoring is a system for checking the study's data at regular intervals over the study period to identify and address issues that could affect the safety of research participants. This requirement is in accordance with 45 CFR 46.111.

The purpose of data and safety monitoring plan is to set forth study team procedures for monitoring/addressing:

- **Participant safety (physical, psychological, etc.)**
- **Data validity**
- **Early stopping (termination) based upon changes in risks and benefits.**

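### The day-3 questions listed in the protocol ask only about current pain and do not match the jaw/neck pain or neuralgia event in the 20% stop rule

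*Protocol*

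**What the plan says.** Both halves of the point are in the protocol's answer to question 6 of Risks, Discomforts, Potential Harms and Monitoring.

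- **The contact.** "Three days following their procedure, the clinical research coordinator will follow up with the study participants and ask the following questions". The listed questions are "Do you have any jaw pain", "Do you have any neck pain" and "Do you have any head pain". All three are in the present tense. None has a look-back period or asks about onset or about pain before the procedure.
- **The script.** "A telephone script that the CRC will use during these interactions has been uploaded". Its text is not among the documents at hand.
- **The rule.** "If 20% of patients in the SAM intervention arm report pain or neuralgia to their jaw/neck following the procedure", the study stops and the protocol is reviewed at once. This is the only numerical stopping criterion in the protocol.
- **The anticipated harm.** Question 1 of the same section says: "There is a minimal risk of minor pain or discomfort following the procedure resulting from the foam pad placement". It also lists jaw and neck pain.

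The answer names no source for the 20% count other than this contact.

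**The concern.** A stop rule works only if the data collected measure the event that the rule names. Here the listed questions and the rule differ in three ways.

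1. **Time window.** The questions measure pain present on day 3. The rule appears to count pain arising at any time after the procedure. Pad or positioning soreness that cleared by day 2 would properly be answered no.
2. **Baseline.** A patient with long-standing neck or jaw pain would properly answer yes. The exclusion criteria cover cervical spine injury, instability and collars, but not chronic neck or jaw pain. Consent may be taken in a preoperative neurosurgery clinic, so some background pain is plausible, although the protocol gives no rate.
3. **Content.** Neuralgia is in the rule but is not asked by name. Head pain is asked but is not in the rule.

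Safety is part of the first specific aim. Conversions to general anesthesia are also a safety measure, but they have no numerical threshold and do not capture jaw or neck pain.

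**Working it through.** **Step 1: what the call and the rule cover.**

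| Feature | Listed day-3 questions | Stop rule |
|---|---|---|
| Time window | Now, on day 3 | After the procedure |
| Jaw pain | Asked | Counted |
| Neck pain | Asked | Counted |
| Neuralgia | Not asked by name | Counted |
| Head pain | Asked | Not counted |
| Onset or prior pain | Not asked | Not addressed |

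**Step 2: which reading of the rule is more natural.** The phrase about the procedure could describe when the pain occurs or when it is reported. Question 1 of the same section uses the same phrase for when pad-related pain occurs. That favours the first reading without settling it.

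**Step 3: inputs for an illustration.**

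- SAM arm size: 20 (sample size justification).
- Threshold: 20% (question 6). The protocol gives no derivation of it, so there is no figure to reproduce. At full enrolment 0.20 × 20 = 4 patients, and the trigger is taken as at least 4 of 20.
- Assumptions, because the protocol gives no values: the true rate of pain after the procedure, the share still in pain on day 3, and the rate of pre-existing pain.

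**Step 4: formula.** P(trigger) = 1 − Σ C(20,k) p^k (1−p)^(20−k), summed over k = 0 to 3, where p is the probability that a patient answers yes.

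**Step 5: resolved pain is missed.** If a proportion r has pain after the procedure and a share s of those still has it on day 3, full capture gives p = r and the listed questions give p = r × s.

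| Assumed r | Full capture | s = 75% | s = 50% | s = 25% |
|---|---|---|---|---|
| 10% | 0.133 | 0.058 | 0.016 | 0.001 |
| 20% | 0.589 | 0.352 | 0.133 | 0.016 |
| 30% | 0.893 | 0.690 | 0.352 | 0.058 |
| 40% | 0.984 | 0.893 | 0.589 | 0.133 |

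For example, r = 30% and s = 50% give p = 0.30 × 0.50 = 0.15, and the trigger probability falls from 0.893 to 0.352.

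**Step 6: pre-existing pain is counted.** With no device-related pain and background pain at rate b, p = b. The trigger probability is 0.016, 0.133, 0.589 and 0.893 for b = 5%, 10%, 20% and 30%.

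Steps 5 and 6 push in opposite directions, so the calculation shows no net direction.

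**The case against.** Several objections carry weight.

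- **The script is unseen.** It is a separate, approved document and may already ask about onset, earlier pain or nerve symptoms. A reader might infer that the call itself omits these items. The protocol supports that only for the questions it lists. This stands as a limit on the point.
- **The rule can be read otherwise.** If the phrase describes when pain is reported, the call and the rule share one time point and the timing gap goes. Counting only pain that persists to day 3 would be a defensible choice. The baseline gap and the differences over neuralgia and head pain would remain.
- **There is another safety route.** A reader might infer that this call is the only way the device's anticipated harm can surface. That goes too far: the DSMB meets monthly and reviews unblinded adverse events. The protocol does not, however, tie that review to the 20% count.
- **Pre-existing pain would not simply end the trial.** The consequence is a stop with immediate review. Prior conditions are taken from the medical record, so that review could identify documented chronic pain. Nothing in the rule requires it to.
- **Both arms appear to be called.** The text refers to study participants generally, so standard-of-care answers could indicate background pain. The rule nevertheless uses the SAM arm alone.
- **The content differences are the weaker part.** Jaw or neck neuralgia present on day 3 would probably be reported as pain, and asking about head pain without a trigger is simply extra safety information.
- **The probabilities are illustrative.** Every pain rate is assumed, and each figure is at full enrolment, when a stop would protect few patients. They do not describe the rule during accrual.

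**Conclusion.** The point holds as a measurement inconsistency. The listed questions do not establish whether a patient has met the stop rule. They do not ask when pain began or whether it was there before, on either reading of the rule. On the more natural reading they also miss pain that has resolved by day 3.

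The effect can be material in either direction. Under an assumed 30% rate of post-procedure pain, the trigger probability ranges from 0.89 with full capture down to 0.06 if a quarter of those affected still have pain on day 3. With no device effect and an assumed 10-20% background rate, it is 0.13-0.59. These figures rest on assumed rates, 20 evaluable SAM patients and a trigger of at least 4. They show sensitivity to the definition; they do not estimate what will happen.

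The documents do not show that the actual call is deficient, since the script may fill part of the gap. Nor does the point bear on whether 20% is the right threshold.

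**What to change.** Reconcile the listed questions, the uploaded script and the stop rule so that all three name the same event and the same time window. The same day-3 call can supply what is needed by asking:

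- whether there has been any jaw, neck or head pain, or any nerve symptom there, since the procedure;
- when it started;
- whether it is still present;
- whether it was present before the procedure.

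The protocol should then state which answers count toward the trigger, including how pre-existing pain, resolved pain, neuralgia and head pain are treated. Those choices and the threshold belong to the sponsor. If the script already contains these items, it is enough to bring the protocol's list and the rule into line with it.

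The cost is a revised script and a few extra form fields, with no added contact. The drawback is reliance on recall over three days.

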View	[name]	Principal Investigator	Project Coordination Study Design		Experience - Research Experience - Clinical Education and/or Professional Preparation		yes

2. Identify all independent investigators and key personnel at non-VCU sites who will be engaged in this study AND who DO NOT have IRB approval for this study from their own institution.

	Name	Roles	Responsibilities - Other	Responsibilities - Other	Qualifications - Other	Qualifications - Other	COI Investigator
--	------	-------	--------------------------	--------------------------	------------------------	------------------------	------------------

There are no items to display

3. If independent investigators or community engaged investigators are listed above, describe the human subjects training these individuals will complete and the process that will be used to ensure that all persons assisting with the research are adequately informed about the protocol and their research related duties and functions:

4. * Upload a CV or Biosketch for the PI, Medically/Psychologically Responsible Investigators and the lead Student/Trainee Investigators. Do not upload CVs or Biosketches for other individuals.

Conflict of Interest

The PI should ask the questions on this page of all research personnel who are engaged in the research, including subrecipient investigators and personnel.

1. * To the best of your knowledge, do you (as PI) or any other engaged individual have a financial interest related to this study?

Financial interest include utilizing your licensed intellectual property in the study; serving as a paid consultant, or advisory board member, or officer/director with a related entity; and equity or business ownership in a company that is related to this project

Yes No

2. * To the best of your knowledge, do you (as PI) or any other engaged individual have a non-financial interest related to this study?

Non-financial Interests could include such things as:

- utilizing your unlicensed intellectual property in the study,
- serving as an unpaid advisory board member or officer/director with a related entity, and
- equity or business ownership in a company that has yet to make a profit and is related to this project
- conflict of time/effort,
- personal and professional relationships/affiliations,
- intellectual passions or personal beliefs
- other factors that could create bias in the study

Yes No

3. * Describe any If Yes, provide:

- Name(s) of the engaged individual(s) with a related non-financial interest
- Brief description of the non-financial interest

Any individual named here should also complete a Financial Interest Report (FIR) in the Activity and Interest Report System (AIRS), even if they were not initially designated as a 'COI Investigator.' Ensure that all designated 'COI investigators,' including the PI, and any others listed here with related interests are up to date in the AIRS (<https://airs.research.vcu.edu>)

[name] and [name] serve as unpaid advisory board members, as product consultants, for the SAM device. They both have a royalty agreement with Atlantic Wave Holdings, LLC, the holding company that owns the device.

4. Describe any institutional conflict of interest that you or any member of the research team are aware of that pertains to this research:

An institutional conflict of interest is a situation in which financial interests of the University or University leadership may affect research activities at VCU.

None.

ID: HM20022338

View: SF2 - Other VCU Requirementsv2

Other VCU Requirements

This page asks questions on behalf of other ancillary offices, committees and departments at VCU regarding institutional requirements that could apply to this research. In some cases, these requirements could also impact the consent process or other aspects of the IRB's review.

Based upon answers provided earlier in this form, certain ancillary sections below may not have questions displayed if those requirements are not applicable to this study.

1. Cost Coverage Analysis

Information on coverage analysis requirements and processes can be found through VCU's Clinical Research Compliance Program at <https://research.vcu.edu/human-research/clinical-research/vcu-clinical-research-coverage-analysis/>

1. * VCU requires that all clinical research studies be evaluated to determine if a Coverage Analysis is required. Has your study been evaluated by an institutionally designated Coverage Analysis Specialist?

Yes

No

Not Applicable

2. ClinicalTrials.gov Program & OnCore

For guidance, see <https://cctr.vcu.edu/support/consultation/clinical-trials-gov/> or email [contact]

1. * Is this a Clinical Trial?

Yes No

2. * ThePI acknowledges awareness of the following requirements for posting clinical trial consent forms:

- Each clinical trial under the 2018 Common Rule that is conducted or supported by a Federal department or agency must post one IRB-approved consent form that was used to enroll subjects on a publicly available Federal website [45 CFR 46.116(h)].

- When engaged in multi-site research, the VCU PI is responsible for confirming with the lead site who is responsible for posting the informed consent form.

- When VCU is the lead site, the VCU PI is responsible for posting the informed consent form (unless the federal department or agency will post it).

Yes No

3. Community Engagement

For more information, see <https://community.vcu.edu/>

1. * Is this a community engaged research study? (See help text for definitions)

Yes

No

4. Family Educational Rights and Privacy Act (FERPA) Requirements

For guidance, see <https://rar.vcu.edu/records/family-educational-rights-and-privacy-act/>

1. * Does this study involve obtaining information from VCU students' educational records (see help text)?

Yes

No

5. Research Data Privacy Requirements

Contact the VCU Research Data Privacy Office with questions: <https://research.vcu.edu/integrity-and-compliance/compliance/research-data-privacy/>

1. * Does this study involve the VCU site (regardless of the IRB of record), or any sites under the VCU IRB's oversight, obtaining data in, or from, a foreign country?

Yes No

2. If yes, list the country/countries:

3. * Does this study involve the VCU site (regardless of the IRB of record), or any sites under the VCU IRB's oversight, obtaining data in, or from, the European Economic Area? (see Help Text for list of countries included in the EEA)

Yes No

6. Information Security

For guidance, see <https://ts.vcu.edu/askit/essential-computing/information-security/>

1. * Using the VCU Data Classification Tool, please determine the appropriate data classification category for the data that will be collected or used in this research.

Note: if the data falls into Category 1, a data security management plan is required by University Information Security Office.

See help text for information on accessing the VCU Data Classification Tool, and for information on creating a data security management plan.

Category 1: all data that require breach notifications in the event of improper release, including personally identifiable information covered by HIPAA and Commonwealth of Virginia regulations.

Category 2: all proprietary data that if improperly released has the potential to cause harm to the institution, its mission or its reputation that do not require breach notifications.

2. * I confirm use of the VCU Data Classification Tool at <https://go.vcu.edu/dataclassification> in determining the data classification category selected in Question 1:

Yes

No

3. * The PI is aware that if the study's data is classified as Category 1, a Data Management Plan must be created. See <https://ts.vcu.edu/askit/essential-computing/information-security/data-management-system/>

Yes No

7. Massey Cancer Center Protocol Review and Monitoring Committee (PRMC)

For guidance, see <https://www.massey.vcu.edu/research/protocol-review/>

1. * Does this study involve any of the following?

- Research involving patients with cancer, their families or their health care providers
- Research involving cancer screening, diagnosis or prevention
- Secondary data collected from cancer patients or their medical records
- Cancer-related surveys (e.g., attitudes about risk, prevention and treatment) of the general population

Yes

No

8. VCU ONETRAC Protocol Review Oversight Committees (PROCs) For guidance, see <https://onetrac.vcu.edu/>

1. * Does this study involve research with any of the following?

- VCU Health System patients

- VCU Health System facilities

- VCU Health System data Yes

No

If Yes, upload documentation of approval or review by the PROC in this study's topic area.

9. VCU Health Department of Patient Centered Services

1. * Does your study involve a satisfaction survey administered to VCUHS patients (*See Help Text):

Yes

No

Not Applicable

10. VCU Faculty-Held IND or IDE

For guidance, see <http://go.vcu.edu/indide>

11. VCU Health System locations

1. * Will research activities occur in patient care areas of the VCU Health System (including at CHoR, Community Memorial Hospital, Tappahannock Hospital, VCU Medical Center and Massey Cancer Center)?

Yes

No

2. * The PI has reviewed and agreed to comply with the VCU Health System Research in Patient Care Areas policy (https://research.vcu.edu/compliance_program/vcuhs_policies.htm):

Yes

No

12. VCUHS Department of Pathology

Learn more about requesting and establishing an account with Pathology here: See

<https://pathology.vcu.edu/research-services/>

1. * I have contacted VCUHS Department of Pathology to determine feasibility if my study involves the following:
- Storage of Microbiology isolates
 - New instrumentation provided by clinical trial/study sponsor, or
 - Non-routine specimen processing (examples include but aren't limited to the following: addition of reagents to samples/aliquots, buffy coat processing, DNA sample processing)

Yes

No

N/A - my study does not involve any of the listed processes.

2. * If my study involves specimen retrieval from the Pathology laboratory, I have established a process with Pathology to deidentify and retrieve specimens.

Yes

No

N/A - my study won't involve specimen retrieval from Pathology

13. VCU Institutional Biosafety Committee (IBC)

To contact the Biosafety Office see their website at: <https://research.vcu.edu/integrity-and-compliance/compliance/regulatory-committees/>

1. * Does this project involve any of the following biohazardous agents?
- Integrating viruses (viruses that may integrate into the patients' genome)
 - Nonintegrating viruses (viruses that express proteins within patients' cells)
 - Expression or administration of biological toxins
 - Biological agents (bacteria, fungi, viruses, etc.)
 - Introduction or expression of rDNA or synthetic nucleic acids

- Use of a product (e.g., monoclonal antibodies) produced from virally infected mammalian cells

Yes No

14. VCU Radiation Safety Committee (RSC)

To contact the Radiation Safety Section see their website at: <https://research.vcu.edu/integrity-and-compliance/compliance/regulatory-committees/>

1. * Does this study involve radiation exposure and/or scans involving radiation (e.g.: PET, MRA, CT, DXA, nuclear medicine, etc.)?

Yes

No

15. VCU Scientific Review Committee (SRC)

For guidance, see <https://ctr.vcu.edu/support/consultation/scientific-review-committee/>

1. * Has this human subjects protocol (not the grant application) already been reviewed by the funder of a sponsored project (e.g. a federal, state or non-profit funding sponsor)?

Yes

No

Based upon your responses, this study will be routed to the VCU Scientific Review Committee (SRC) when it is submitted. After SRC review is completed, the IRB will receive the study.

16. Upload any documents requested in the questions above:

ID: HM20022338

View: SF2 - HIPAA

HIPAA

HIPAA Privacy Board Requirements

For guidance, see <https://www.vcuhealth.org/our-story/who-we-are/compliance-services/compliance-services>

- * Select the source of the Individually Identifiable Health Information. See help text for definitions.
 - PHI associated with or derived from (i.e. obtained from or entered into) VCU Health medical records or VCU Dental Care records
 - Research Health Information (RHI) created or received by a study and kept solely in study records (e.g. self reported or the result of research tests and not entered into health records)
 - PHI associated with or derived from (i.e. obtained from or entered into) a non-VCU HIPAA covered entity's health records
- * Summarize the types of health information that will be obtained or used in this research. Do not describe only the identifiers that you will collect or use during the study.

A patient's age, sex, weight, BMI, medications, and prior medical history will be obtained in this research.
- * Describe the source(s) of the protected health information (e.g. which clinical databases):

Information will be obtained from Cerner/Epic.
- * Does the PI certify that this study's access to and use of the protected health information is limited to the minimum amount necessary to be able to effectively conduct the research?

Yes No

5. * Select all pathways this research will employ to use or access PHI (selections will branch):

- De-Identified Data (none of the 18 identifiers are recorded or associated with the research data)**
- Limited Data Set
- Waiver of Authorization
- Partial Waiver of Authorization (temporary waiver for recruitment purposes and/or waiver of some elements of Authorization)
- Signed Authorization Combined with Consent Form
- Signed Authorization as Stand-Alone Form

ID: HM20022338

View: SF2 - De-Identified Data

De-Identified Data

1. * The PI certifies that the data collected or used in this study does not contain any of the following identifiers and the PI does not have access to a key to link a code to the identifying information:

- 1) Names
- 2) Geographic Locators Below State Level
- 3) Social Security Numbers
- 4) Dates, except years and ages >89
- 5) Phone Numbers
- 6) Facsimile Numbers
- 7) Email Addresses
- 8) Medical Record Numbers
- 9) Device Identifiers
- 10) Biometric Identifiers
- 11) Web URLs
- 12) IP Addresses
- 13) Account numbers
- 14) Health Plan Numbers
- 15) Full Face Photos or Comparable Images
- 16) License /Certificate Numbers
- 17) Vehicle ID Numbers
- 18) Other Unique Identifier

 Yes No**2. * Select which method of de-identification applies to the data used for this study.**

- All Identifiers Removed (Safe Harbor)**
- Expert determination Verifying No Possibility of Re-Identification

3. If statistical analysis will be done to determine data is not identifiable, upload attestation from the statistician.

ID: HM20022338

View: SF2 - Institutional Requirements Complete

Institutional Requirements Complete

Protocol Progress:

- ? INITIAL SETUP
- ? BACKGROUND, RATIONALE & GOALS
- ? RESEARCH PLAN
- ? CONSENT PLAN
- ? RISKS, PRIVACY & CONFIDENTIALITY
- ? POPULATIONS WITH SPECIAL CONSIDERATIONS
- ? INSTITUTIONAL REQUIREMENTS
- ? DOCUMENTS

Click Continue below to go to the next section

ID: HM20022338

View: SF2 - Documents

Documents

1. Upload any documents that the VCU IRB will need to conduct a review of this submission:
A list of potential documents is given in the help text.

NOTE: The delete function should only be used if an incorrect document is uploaded or added to the system AND that document has not been reviewed and approved by the IRB. Do NOT delete documents that the IRB previously reviewed and approved.

Once you have uploaded a document to RAMS-IRB, any changes to that document (i.e. different versions of the same document) should be added to the IRB submission by using the Update button. To provide updated documents, follow these steps:

- Click the Update button located to the left of the document to be updated.
- In the Add Document window, click the Choose File or Browse button, select the file you are adding, and click on the Open button.
- Click OK to close the Add Document window, and the system will upload the revised document. RAMS-IRB will automatically provide a version number for the document.

To access previous versions of a document in RAMS-IRB you must use the History link associated with the document.

- Click the View or Update button located to the left of the document you wish to access.
- In the Add/View Document window, click the "History" hyperlink located to the right of the file name.
- A separate window will open that shows all versions of the document that have been added to RAMS-IRB. Click on any file name to download and view the document.

	Document Name	Document	Version	Date Modified	Uploaded By	Type	Approved
View	SAM Consent Form	Consent Form- IRB Clean Version 10-4-21.pdf	0.06	11/4/2021 12:54 PM	[name]	Consent/Assent/Information Sheet	Yes
View	SAM Device Photograph 2 (without final pads)	SAM device photograph 2.jpeg	0.01	10/12/2021 9:40 PM	[name]	Other	Not Applicable
